11.5.3. Provision of SAE follow-up information

Following reporting of an SAE for a participant, the participant should be followed up until resolution or stabilisation of the event. Follow-up information should be provided using the SAE reference number provided by the Trial Office. Once the SAE has been resolved, all critical follow-up information has been received and the paperwork is complete, a copy of the final version of the completed SAE form must be submitted to the Trial Office and the original kept in the ISF.

11.6. Reporting SAEs to third parties

The independent Data Monitoring Committee (DMC) may review any SAEs at their meetings.

The Trial Office will report details of all SARs (including SUSARs) to the MHRA, Research Ethics Committee (REC), and University of Birmingham (UoB) Research Governance Team (RGT) annually from the date of the Clinical Trial Authorisation, in the form of a Development Safety Update Report (DSUR).

Additionally, the Trial Office will report a minimal data set of all individual events categorised as a fatal or life threatening SUSAR to the MHRA, REC, and UoB RGT within 7 days of being notified. Follow-up information will be provided within an additional 8 days.

All other events categorised as SUSARs will be reported within 15 days of being notified.

Details of all SUSARs and any other safety issue which arises during the course of the trial will be reported to the PIs. A copy of any such correspondence should be filed in the ISF and Trial Master File (TMF).

11.7. Urgent Safety Measures

The Clinical Trials Regulations make provision for the Sponsor and PIs to take appropriate Urgent Safety Measures to protect a research participant from an immediate hazard to their health and safety. This measure can be taken before seeking approval from the competent authorities (MHRA in the UK) and ethics committees of all member states concerned.

If any urgent safety measures are taken, the Trial Office shall immediately, and in any event no later than 3 days from the date the measures are taken, give written notice to the REC and the MHRA of the measures taken and the reason why they have been taken.

12. DATA HANDLING AND RECORD KEEPING

12.1 Source data

Source data is defined as all information in original records and certified copies of original records of clinical findings, observations, or other activities in a clinical trial necessary for the reconstruction and evaluation of the trial. In order to allow for the accurate reconstruction of the trial and clinical management of participants, source data will be accessible and maintained.

Some data variables may be entered directly onto the CRF, these are clearly identified and detailed below in Table 7.

Table 7: Source data in OXYPuF

Data	Source
Participant Reported Outcomes	The original participant-completed CRF is the source and will be stored with the participant's trial record at the trial office.
Lab results	The original lab report (which may be electronic) is the source and will be kept and maintained, in line with normal local practice. Information will be transcribed onto CRFs.
6MWT	The 6 minute walk test or the 1 minute sit to stand test results will be directly transcribed onto the CRF. The CRF is the source data
Clinical event data	The original clinical annotation is the source document. This may be found on clinical correspondence, or electronic or paper participant records. Clinical events reported by the participant, either in or out of clinic (e.g., phone calls), must be documented in the source documents.
Health economics data	Often obtained by interview directly with the participant for transcription onto the CRF. The CRF is source data.
Qualitative interviews	Interviews will be recorded and transcribed clean verbatim for analysis. The recording is the source.
Recruitment	The original record of the randomisation is the source. It is held on BCTU servers as part of the randomisation and data entry system.
Withdrawal	Where a participant expresses a wish to withdraw, the conversation must be recorded in the participants medical records.

12.2 Case Report Form (CRF) completion

The CRFs will include (but will NOT be limited to) the following Forms (see Table 8).

Table 8: Case report forms in OXYPuF

Form Name	Schedule for submission
Consent CRF	At the point of randomisation
Randomisation CRF	At the point of randomisation
Actigraph CRF	At the point of randomisation

Baseline and follow-up CRFs including participant reported outcome measures	As soon as possible after each assessment time point
Serious Adverse Event CRF paper CRF only	If expedited: emailed within 24 hours of site research team becoming aware of event If non-expedited: emailed within 4 weeks of site research team becoming aware of event
Change of status CRF	As soon as possible after the point of reduced participation or death

A CRF is required and should be completed for each individual participant. The data held on the completed original CRFs are the sole property of the respective PIs whilst the data set as a whole is the property of the Sponsor and should not be made available in any form to third parties except for authorised representatives or appropriate regulatory authorities without written permission from the Sponsor.

Data reported on each CRF will be consistent with the source data and any discrepancies will be explained. All missing and ambiguous data will be queried. Staff delegated to complete CRFs will be trained to adhere to the **OXYPuF Work Instruction on CRF completion** which can be found in the **OXYPuF ISF**.

The delegated staff completing the CRF should ensure the accuracy, completeness and timeliness of the data reported. This will be evidenced by signing and dating the CRF.

The following guidance applies to data and partial data:

- Only CRFs provided by the Trial Office should be used.
- Original completed CRFs or true copies should be sent to the Trial Office with copies filed in the ISF.
- Entries should be made in dark ink and must be legible.
- Any errors should be crossed out with a single stroke, the correction inserted and the change initialled and dated.
- Time format – all times should be in accordance with the 24hr clock
- Rounding conventions – rounding should be to the nearest whole number: If the number you are rounding is followed by 5, 6, 7, 8, or 9, round the number up. **Example:** 3.8 rounded to the nearest whole number is 4. If the number you are rounding is followed by 1, 2, 3 or 4, round the number down. **Example:** 3.4 rounded to the nearest whole number is 3
- Trial-specific interpretation of data fields – where guidance is needed additional information will be supplied
- Entry requirements for concomitant medications (generic or brand names) – generic names should be used where possible
- Missing/incomplete data – should be clearly indicated – all blank fields will be queried by the Trial Office
- Repeat laboratory tests – the data used to inform clinical decisions should always be supplied. If a test is repeated it is either to confirm or clarify a previous reading. Confirmatory tests should use the original test values.
- Protocol and GCP non-compliances should be reported to the Trial Office on discovery.

For the OXYPuF trial, all CRFs (with the exception of SAE forms and Participant completed questionnaires), will be completed electronically at site via eCRFs directly onto the OXYPuF database [**<include link>**](#). **SAE forms are completed via paper CRF only at site.** Electronic CRFs (eCRFs) and paper CRFs should only be completed by those who are delegated to do so as evidenced on the **OXYPuF Trial Signature and Delegation log**.

Data should be submitted within a 2 week period of the schedule. If the data has still not been received within 2 weeks then the trial manager will directly contact the site via email to ascertain the reason for the delay. At 8 weeks from expected submission if the data still has not been received this may be escalated to the site's senior management and can trigger a monitoring visit.

In all cases it remains the responsibility of the PI to ensure that the CRF (electronic and paper) has been completed correctly and that the data are accurate. This will be evidenced by the signature of the PI.

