8.2.2.3 Mechanistic

Haemoglobin and haematocrit, which are measures of secondary effects of chronic hypoxia – rises in either would indicate a lack of effectiveness of AOT, or disease progression by way of development of chronic respiratory failure. They are a required safety measure as well, as development of secondary rises in either measure would be an indication for routine oxygen treatment.

Physical activity data will also be obtained via an accelerometer in a subset of 20% of trial participants (n=52; 26 participants from each trial arm), and associated processing software for how many minutes per day somebody is active in terms of intensity of exercise: sedentary; low; moderate; high. Accelerometers will be worn by the participant for 7 days after randomisation prior to commencing the trial allocation. It will then also be worn for 7 days prior to their final trial visit.

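### Section 12.2 tells sites to round CRF values to whole numbers with no exception by variable, which conflicts with its own rule that CRFs agree with source and, depending on units, could strip haematocrit and pH of information

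*Protocol*

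**What the plan says.** Section 12.2 opens its list of CRF conventions with "The following guidance applies to data and partial data". One item states that "rounding should be to the nearest whole number", and its worked examples are "3.8 rounded to the nearest whole number is 4" and "3.4 rounded to the nearest whole number is 3". It names no variable, unit or number of decimals to which the rule does or does not apply. Earlier in 12.2, CRF data are required to be consistent with the source and any discrepancy explained.

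For laboratory results, Table 7 in section 12.1 says "The original lab report (which may be electronic) is the source and will be kept and maintained, in line with normal local practice", and then "Information will be transcribed onto CRFs". Section 8.2.2.3 lists among the mechanistic outcomes "Haemoglobin and haematocrit, which are measures of secondary effects of chronic hypoxia", treats a rise in either as the signal of interest, and adds "They are a required safety measure as well". Section 9 also collects blood gases (only if saturation on air is below 90%), spirometry and gas transfer. The protocol gives no recording units for any of these.

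**The concern.** The item sets a target precision, the whole number, as well as a convention for halves. Several variables reach the CRF from reports that may carry decimals. Where the whole range of a variable spans less than one unit, rounding to integers leaves almost nothing to analyse. Where it spans a few units, rounding adds noise. Haematocrit matters most because it is a named mechanistic and safety measure that is informative through change from baseline.

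There is also a contradiction that does not depend on units. A site that rounds a decimal laboratory value creates a CRF entry that differs from source, and a site that copies the value departs from the rounding item. Sites may resolve this differently, so the same variable could arrive at different precision from different centres.

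**Working it through.** **Step 1. Reproduce the rule.** Half-up rounding is r(x) = floor(x + 0.5). r(3.8) = floor(4.3) = 4 and r(3.4) = floor(3.9) = 3. Both protocol examples reproduce.

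**Step 2. Inputs.** The protocol supplies the rule and the list of variables. It supplies no units, means or SDs, so those below are assumptions, taken as normal distributions and given as ranges.

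**Step 3. Variables that span less than one unit.** The share recorded at the lower integer is Φ((cut − mean)/SD), with the cut at 0.5 for fractional haematocrit and 7.5 for pH. The last column is the correlation of the rounded with the true value.

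| Variable | Mean, SD (assumed) | Calculation | Recorded as | Correlation |
|---|---|---|---|---|
| Haematocrit, L/L | 0.43, 0.03 | Φ(0.07/0.03) = Φ(2.33) | 0 in 99% | 0.26 |
| Haematocrit, L/L | 0.45, 0.05 | Φ(0.05/0.05) = Φ(1.00) | 0 in 84% | 0.66 |
| pH | 7.42, 0.03 | Φ(0.08/0.03) = Φ(2.67) | 7 in 99.6% | 0.19 |
| pH | 7.40, 0.05 | Φ(0.10/0.05) = Φ(2.00) | 7 in 98% | 0.36 |

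The remaining values become 1 (haematocrit) or 8 (pH).

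**Step 4. Variables that span several units.** Rounding to integers adds error with variance close to 1/12. The equivalent sample-size inflation is therefore about 1 + 1/(12·SD²). Simulation with 400,000 draws per variable, using 1/correlation², agrees with this to within about one percentage point.

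| Variable | SD (assumed) | 1 + 1/(12·SD²) | Inflation |
|---|---|---|---|
| FVC, litres | 0.5 | 1 + 1/3.00 | about 33% |
| FVC, litres | 0.8 | 1 + 1/7.68 | about 13% |
| PaCO2, kPa | 0.6 | 1 + 1/4.32 | about 23% |
| PaO2, kPa | 1.0 to 1.5 | 1 + 1/12 to 1 + 1/27 | about 8% to 4% |
| Gas transfer, mmol units | 1.2 | 1 + 1/17.3 | about 6% |
| Haemoglobin, g/dL | 1.4 | 1 + 1/23.5 | about 4% |
| Haematocrit, % | 3 to 5 | 1 + 1/108 to 1 + 1/300 | under 1% |
| Haemoglobin, g/L | 14 | 1 + 1/2352 | negligible |
| FVC, % predicted | 15 | 1 + 1/2700 | negligible |
| Gas transfer, % predicted | 14 | 1 + 1/2352 | negligible |
| Walk distance, m | 100 | 1 + 1/120000 | negligible |

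**Step 5. Bias or noise for FVC in litres.** A true fall of 0.1 L changes the rounded value in about 10% of participants, by 1 L, and in the other 90% not at all. The mean recorded change is 0.10 × 1 + 0.90 × 0 = 0.1 L. The group mean is roughly preserved and precision is lost.

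**Step 6. What is not touched.** By Table 7 the participant-completed form is the source for K-BILD, so sites do not round the responses. The sample size rests on K-BILD alone. The minimisation factors in section 6.4 are centre and three yes/no items.

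**The case against.** The strongest reply is that the item describes how to round where a field calls for it and does not order every value to be rounded. The requirement for consistency with source supports that reading. Section 12.2 also promises further guidance on data fields where needed and refers to a work instruction on CRF completion, and section 12.4 refers to a data management plan. None of these is shown, and any of them may fix decimals. This has weight. However, the protocol does not say that any of them overrides the rounding item, nor when rounding is called for, and the whole-number rule is the only content it gives.

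A second reply is that range checks and central queries (sections 12.4 and 13.2.2) would catch absurd entries. A haematocrit of 0 should be caught. An FVC of 3 L is plausible and would pass.

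A reader might go further and infer that haematocrit, blood gas and lung function data would be destroyed beyond recovery, that derived severity scores would be wrong, and that safety monitoring would fail. The documents do not support this:

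- The severe loss needs fractional haematocrit or pH. Where the protocol mentions an FVC scale (sections 1.1 and 1.2.1), it is a percentage.
- Laboratory reports are retained as source, so the true values survive at site.
- The GAP score is defined and discussed as background, but no outcome, minimisation factor or analysis uses it.
- Blood gases and lung function are collected but are not listed outcomes. The mechanistic outcome pairs haematocrit with haemoglobin, which survives rounding well.
- Rounding the CRF copy does not alter the report held at site, so impaired safety use is not shown.

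**Conclusion.** The point stands as a wrongly stated data-entry rule of minor to moderate severity. Whatever the units, the rounding item conflicts with the consistency requirement in the same section. The size of the loss depends on units the protocol does not give and on the assumed distributions above. It is near total for fractional haematocrit (84–99% recorded as 0) and pH (98–99.6% recorded as 7), partial for litre-scale FVC and PaCO2 in kPa (13–33% equivalent inflation), and small or negligible for the rest. For laboratory results the damage would be confined to the trial database and could be repaired by returning to each site's reports. The primary outcome, sample size and minimisation are unaffected.

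**What to change.** Replace the rounding item in section 12.2 with: *Enter each value in the units and to the decimal places shown on the source report; do not round, except in fields designed as integers.* Set the units and number of decimals for each eCRF field, and align the work instruction with the new sentence. If sites have already entered data under the current rule, query haematocrit, pH, FVC and PaCO2 against source.

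The cost is one sentence and field settings in the database, with no loss to the trial. The change also removes the conflict with the consistency requirement.

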12.3 Participant completed questionnaires

Participant completed questionnaires are completed by participants and are completed using paper questionnaires.

Questionnaires should generally be completed by the participant alone but physical assistance in completing the form can be given by the research staff or the participant's friends and relatives where appropriate. In such circumstances, questions are to be read to the participant verbatim and responses must not be led by the person assisting with the form completion. This requirement must be made clear when the participant's friends and relatives are providing the assistance. Participants should be encouraged to respond to all questions but can refuse to answer any, or all, of the questions should they wish. Where a questionnaire is returned to the local research staff, in person, with some questions unanswered, research staff should clarify with the participant that they have chosen not to respond specifically to the unanswered questions and that they have not simply missed them in error.

These questionnaires should be completed in clinic at baseline. For follow up questionnaires, these can be sent out to the participant via post and then returned to the trials office either directly via a self-addressed envelope or returned to the trials office by the site if a participant completes the questionnaires in clinic.

12.4 Data Management

Processes will be employed to facilitate the accuracy and completeness of the data included in the final report. These processes will be detailed in the trial specific Data Management Plan and include the processes of data entry, data queries and self-evident corrections on trial data.

Data entry will be completed by the sites via a bespoke BCTU trial database. The data capture system will conduct automatic range checks for specific data values to ensure high levels of data quality. Queries will be raised using data clarification forms (DCFs) via the trial database, with the expectation that these queries will be completed by the site within 30 days of receipt. Overdue data entry and data queries will be requested on a monthly basis.

12.5 Self-evident corrections

The below self-evident corrections will be permitted by the Trial Office:

Contingent fields: When a response to a question determines, to a degree, the response required by a second question, then conflicts in the responses can be resolved by the data entry clerk. E.g., Has the person had procedure "x"? If yes, state type. If the response to the first question is "no", yet the type of procedure is stated, it is self-evidently true that the initial response was incorrect.

Changes to administrative notes and reference numbers: When new information becomes available such that a reference number does not accurately reflect the sequence of CRFs received e.g., an SAE form is received for an incident which occurred prior to an already reported incident, then it is appropriate to change the reference number provided no DCFs have been raised using the original number. Similarly, any notes relating to the participant care

which have an impact on the administration process, but not the data fields themselves, can be changed as appropriate.

12.6 Data security

UoB has policies in place, which are designed to protect the security, accuracy, integrity and confidentiality of Personal Data. The trial will be registered with the Data Protection Officer at UoB and will hold data in accordance with the Data Protection Act (2018 and subsequent amendments). The Trial Office has arrangements in place for the secure storage and processing of the trial data which comply with UoB policies.

The Trial Database System incorporates the following security countermeasures:

Physical security measures: restricted access to the building, supervised onsite repairs and storages of back-up tapes/disks are stored in a fire-proof safe.

Logical measures for access control and privilege management: including restricted accessibility, access controlled servers, separate controls of non-identifiable data.

Network security measures: including site firewalls, antivirus software and separate secure network protected hosting.

System management: the system will be developed by the Programming Team at the Trial Office, and will be implemented and maintained by the Programming Team.

System design: the system will comprise of a database and a data entry application with firewalls, restricted access, encryption and role based security controls.

Operational processes: the data will be processed and stored within BCTU.

System audit: The system will benefit from the following internal/external audit arrangements:

1. Internal audit of the system
2. Periodic IT risk assessment

Data Protection Registration: UoB's Data Protection Registration number is Z6195856.

12.7 Archiving

All records created by following trial procedures and all documents listed in guidance relating to the conduct of the trial must be retained and archived for the specified period.

The TMF will be stored at BCTU for at least 3 years after the end of the trial. Long-term offsite data archiving facilities will be considered for storage after this time; data will be stored securely and confidentially for at least 25 years. BCTU has standard processes for both hard copy and computer database legacy archiving.

It is the responsibility of the PI to ensure all essential trial documentation and source documents (e.g. signed ICFs, Investigator Site Files, participants' hospital notes, copies of CRFs etc.) at their site are securely retained for at least 25 years. Archiving will be authorised by BCTU on behalf of UoB following submission of the end of trial report. No documents should be destroyed without prior approval from the BCTU Director or their delegate.

13. QUALITY CONTROL AND QUALITY ASSURANCE

13.1 Site set-up and initiation

The CI is required to sign a UoB CI agreement to document the expectations of both parties. The UoB CI agreement document must be completed prior to participation. The CI is required to sign a Clinical Trials Task Delegation Log which documents the agreements between the CI and BCTU. In addition all PIs will be asked to sign the necessary agreements including a Site Signature and Delegation log between the PI and the Trial Office and supply a current CV

and GCP certificate. All members of the site research team are required to sign the **Site Signature and Delegation Log**, which details which tasks have been delegated to them by the PI. The Site Signature and Delegation Log should be kept up to date by the PI. It is the PI's responsibility to inform the Trial Office of any changes in the site research team.

Prior to commencing recruitment, each recruiting site will undergo a process of initiation, either a meeting or a teleconference, at which key members of the site research team are required to attend, covering aspects of the trial design, protocol procedures, adverse event reporting, collection and reporting of data and record keeping. Sites will be provided with an ISF containing essential documentation, instructions, and other documentation required for the conduct of the trial.

